8.1.11 Calibration of Equipment

The investigator or qualified designee has the responsibility to ensure that any device or instrument used for a clinical evaluation/test during a clinical study that provides information about inclusion/exclusion criteria and/or safety or efficacy parameters shall be suitably calibrated and/or maintained to ensure that the data obtained is reliable and/or reproducible. Documentation of equipment calibration must be retained as source documentation at the study site.

8.1.12 Dispense Glucose Meters, Blood Glucose Assessment Tools, and SMBG Instructions

Glucose meters will be supplied to all participants (if needed) and both the participant and legally acceptable representative will be instructed on the procedure for performing FSG measurements. At a minimum, the participant and legally acceptable representative will be instructed to monitor and document FSG values (1) once daily with at least 2 fasting (before breakfast) measurements each week, (2) whenever the participant has symptoms of hypoglycemia (Section 6.5.1), and (3) during intercurrent illnesses. For participants on insulin (as background therapy or as rescue/intensification during the study), the investigator will counsel the participant and legally acceptable representative on the recommended frequency of home glucose monitoring based on locally accepted clinical practice guidelines. The Blood Glucose Assessment Tools should also be completed when the participant is away from home.

Note: The Blood Glucose Assessment Tools do not need to be dispensed during Discontinuation/Withdrawal from the Study Visit.

8.1.13 Instruct on Hypoglycemia Symptoms and Management

The site will review the symptoms and management of hypoglycemia with the participant and legally acceptable representative. The site will counsel the participant and legally acceptable representative to immediately perform an FSG measurement if any symptoms occur that may be related to hypoglycemia (eg, weakness, dizziness, shakiness, increased sweating, palpitations, or confusion), but also to avoid delay in treating these symptoms.

The participant and legally acceptable representative will be instructed to complete the provided blood glucose assessment tools provided for any symptomatic episodes he or she believes may represent hypoglycemia. If an FSG has been obtained before or shortly (ie, within a few minutes) after treating, the value will be recorded in the blood glucose assessment tools. In addition, participants and legally acceptable representatives will be instructed to record any FSG values ≤70 mg/dL (3.9 mmol/L) on the blood glucose assessment tools regardless of the presence of clinical symptoms.

Participant and legally acceptable representatives will be instructed to contact the investigational site to report:

- Any episode of possible hypoglycemia resulting in symptoms
- Any episode of hypoglycemia for which assistance was required (ie, severe hypoglycemia, details provided on the blood glucose assessment tools)
- Any episode of FSG \leq 70 mg/dL (3.9 mmol/L) with or without symptoms

Note: As indicated, the participants will record symptoms and/or FSG measurements that they believe are related to hypoglycemia on the blood glucose assessment tools with the assistance of the legally acceptable representative. Each episode will be evaluated by the investigator and recorded on the appropriate eCRF. For episodes determined to be hypoglycemia (symptomatic or asymptomatic), and for all glucose values ≤70 mg/dL (3.9 mmol/L), regardless of whether they are considered an AE, the HA eCRF must also be completed. Each event of symptomatic hypoglycemia must be reported as an AE on the AE eCRF. Each episode of asymptomatic hypoglycemia considered by the investigator to be an AE will also be reported on the AE eCRF (refer to Appendix 3 for guidance on reporting).

Participants on Background Insulin Therapy

The dose of insulin will be down-titrated or interrupted if, in the opinion of the investigator, the hypoglycemia occurred in the absence of a readily apparent cause or precipitating factor. Further management of insulin doses will be at the investigator's discretion.

8.1.14 Second Randomization

At **Visit 5/Week 12**, all participants will have an FS A1C measured at the site (Section 8.3.8.1). Participants will undergo a second randomization as outlined in the SoA *if* their FS A1C is \geq 7.0% (53 mmol/mol). At this second randomization, eligible participants on ertugliflozin 5 mg will be assigned to continue on the 5 mg dose or up-titrate to the ertugliflozin 15 mg dose in a 1:1 ratio. Eligible participants in the placebo group will participate in the second randomization, but all will remain on placebo and be mock-titrated to preserve blinding. Note: The up-titration criteria for participants on insulin will include a FFSG \geq 110 mg/dL (6.1 mmol/L) in addition to A1C \geq 7.0% (53 mmol/mol) at **Visit 5/Week 12**. Participants who do not meet the threshold(s) for a second randomization will continue on ertugliflozin 5 mg/placebo. If a participant discontinues study medication before **Visit 5/Week 12**, the second randomization (and related assessments) should not be performed.

At **Visit 5/Week 12**, a second allocation number will be randomly assigned by the IRT system for participants on ertugliflozin 5 mg who meet up-titration criteria. During the study, only the unblinded statistician will have access to this allocation number and its associated treatment assignment. Participants who undergo the second randomization will retain their initial randomization number assigned at **Visit 3/Day 1/Randomization** to uniquely identify them by blinded personnel during the study.

The unblinded statistician who supports the DMC described in Section 9.7 will review the number of participants randomized to the ertugliflozin 5 mg and ertugliflozin 15 mg group at the **Visit 5/Week 12** second randomization and throughout the study. Based on the distribution of participants within the ertugliflozin 5 mg and 15 mg arms, the randomization ratio for the second randomization at **Visit 5/Week 12** may be adjusted in order to achieve approximately 30 participants in the ertugliflozin 15 mg arm.

8.2 Efficacy Assessments

8.2.1 Body Weight

Body weight will be measured using a standardized digital scale. Details on measuring body weight are below.

- Weight will be measured *in duplicate* throughout the study, after voiding (ie, forced void), and while wearing only a gown and underwear (no street clothes, no shoes or socks). Investigator sites without access to gowns will weigh participants in light clothing.
- Participants will be instructed to step gently onto the scale, place both feet together in the
 center of the scale and stand straight with eyes directed ahead. Participants will be
 instructed to stand still and not sway. Measurements will be recorded after the weight has
 stabilized.
- The 2 measurements will be recorded in the source documents. If the 2 measurements differ by more than 0.2 kg or by 0.4 lb, (1) check the participant to ensure proper positioning as indicated above (2) a different set of duplicate measurements must be obtained, and the 2 new measurements will be recorded in the source documents. The average of the 2 measurements will be recorded in the eCRF.

Follow the manufacturer's manual for accuracy checks of the scale as required. Contact the Sponsor if supplies are required to perform accuracy checks, or if calibration is required, or for a replacement if the scale is malfunctioning.

8.2.2 Waist Circumference

Tension-controlled measuring tapes will be used to measure waist circumference. The tape measure will be a non-stretching, non-metallic retractable tape.

The tape is placed around the participant's trunk at the appropriate level for waist measurement. The tape's "zero line" is aligned alongside of the tape graduations on the Metric side of the tape. The zero end of the tape is held in the left hand above the remaining part of the tape held by the right hand. The measurement is read next to the tape's "zero line" and recorded in centimeters to the nearest millimeter.

Waist circumference will be measured according to the National Health and Nutrition Examination Survey (NHANES) III protocol. Measuring tapes may be provided by the

Sponsor. It is advisable that the participant's waist be measured by the same study personnel at each visit to maintain consistency. Waist circumference will be measured after voiding, in gown, underwear and socks but without shoes.

To define the level at which waist circumference is measured, a bony landmark is located and marked. The participant stands and the examiner, positioned at the right of the participant, palpates the upper hip bone to locate the right iliac crest. Just above the uppermost lateral border of the right iliac crest, a horizontal mark is drawn using a black pen, and then crossed with a vertical mark on the midaxillary line. The measuring tape is placed in a horizontal plane around the abdomen at the level of this marked point on the right side of the trunk. The plane of the tape is parallel to the floor and the tape is snug but does not compress the skin. The measurement is made at the end of normal minimal respiration (in duplicate). Measurements will be collected until 2 consecutive measurements do not differ by more

than 1 cm. The average of these 2 measurements will be reported.

8.2.3 Height

Height will be measured without shoes, using a stadiometer or other appropriate device.

Standing height will be assessed through maximum vertical stature for persons who can stand unassisted. Hair ornaments, barrettes, braids, jewelry, or cornrows will be moved or removed from the top of the head before the measurement is taken.

A fixed stadiometer with vertical backboard, fixed floorboard and movable headboard will be used. Participants will stand with the heels of their feet against the vertical backboard with feet pointing outward at approximately a 60-degree angle. Body weight will be distributed evenly with both feet flat on the floor. The examiner will check several contact points with the vertical backboard, including heels, buttocks, shoulder blades, and the back of the head. This may be difficult for participants with certain body shapes. However, the head should be in the Frankfort plane (an imaginary line from the ear canal to just below the lower orbit of the eye will be parallel to the floor). Participants will be looking straight ahead and be asked to take a deep breath and stand tall. Once the participant is positioned, the headboard or a flat ruler will be placed on top of the head, with sufficient pressure to compress the hair. The measurement is recorded in centimeters (cm), to the nearest millimeter (mm). Measurements will be collected until 2 consecutive measurements do not differ by more than 2.5 cm from each other. The final height measurement must be recorded. Some participants may have physical conditions that may limit the ability to measure height accurately (eg, kyphosis). In such cases, height will be measured to the best of the examiner's ability, and a note will be made of the condition.

8.2.4 **BMI Percentile**

The following equation will be used to calculate BMI:

Body weight in kilograms (height in meters) 2 BMI =

Sites will follow their approved country-specific BMI-for-age percentile charts. If none are available, refer to Appendix 8.

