95% CI for **Treatment Descriptive** Tier Safety Variable/Endpoint p-Value **Comparisons Statistics** Tier 1 AEs of genital mycotic infection (gender X X X specific) AEs of hypovolemia X X X X X X Events of symptomatic hypoglycemia X X AEs of UTI X Tier 2[†] Episodes of severe hypoglycemia X X X X Requiring medical assistance X X X X Not requiring medical assistance X Episodes of documented hypoglycemia X X AE summary measures X X X Specific AEs ‡ or PDLCs (incidence ≥ 8 participants in the combined ertugliflozin group or ≥ 2 participants in the placebo group) X Tier 3 Specific AEs[‡] or PDLCs (incidence <8 participants in combined ertugliflozin group or <2 participants in the placebo group) Additional hypoglycemia endpoints X Change from baseline results (labs [including X bone biomarkers], vital signs, and abdominal ultrasounds) X Growth velocity and Tanner Staging

Table 9 Analysis Strategy for Safety

AE = adverse event; CI = confidence interval; PDLC = predefined limits of change; UTI = urinary tract infection; X = results will be provided.

Analysis of Hypoglycemia

For the hypoglycemia endpoints described in Section 9.4.2, the analyses of hypoglycemia will be performed separately for participants on a background of insulin and for participants not on a background of insulin at screening. Analyses of hypoglycemia combining participants on and not on a background of insulin are not planned.

[†] Endpoints listed here will qualify for Tier 2 only if the incidence is ≥8 participants in the combined ertugliflozin group or ≥2 participants in the placebo group.

[‡] Includes only those endpoints not prespecified as Tier 1 or not already prespecified as Tier 2 endpoints.

Tier 1 endpoints for hypoglycemia are the percentages of participants experiencing 1 or more episodes of symptomatic hypoglycemia.

Tier 2 endpoints for hypoglycemia are the percentages of participants experiencing 1 or more episodes of documented or severe hypoglycemia defined above. Summaries will be provided for all episodes.

Tier 3 endpoints for hypoglycemia are the percentages of participants with documented hypoglycemia as defined above:

- by lowest reported glucose category (<54 mg/dL [3.0 mmol/L], ≤70 mg/dL [3.9 mmol/L]); and
- by number of episodes.

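### Height is read at least twice but only the final reading is recorded, unlike weight, waist and blood pressure; this adds avoidable random error to descriptive and exploratory growth and size measures

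*Combined protocol and SAP*

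**What the plan says.** Section 8.2.3 (Height) specifies a fixed stadiometer, positioning checks and reading to the nearest millimetre. On repetition it says "Measurements will be collected until 2 consecutive measurements do not differ by more than 2.5 cm from each other", so every participant has at least two readings per visit. On what to keep, it says only "The final height measurement must be recorded". No averaging rule for height was found elsewhere in the document.

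The neighbouring sections treat repeated readings differently:

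- Body weight (Section 8.2.1) is measured in duplicate and a new pair is required beyond 0.2 kg. Then "The average of the 2 measurements will be recorded in the eCRF".
- Waist circumference (Section 8.2.2) is repeated until two consecutive readings agree within 1 cm. Then "The average of these 2 measurements will be reported".
- Blood pressure and pulse (Section 8.2.5) are taken in triplicate and the average of the three goes in the eCRF.

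Height feeds three analysed measures. Table 9 in Section 9.6.2 lists "Growth velocity and Tanner Staging" under Tier 3. Table 6 in Section 9.4.1 lists change in BMI percentile and in waist-to-height ratio as exploratory endpoints.

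**The concern.** Of the body-size and vital-sign measures that the protocol repeats, height is the only one whose repeats are not averaged, and no reason is given. The second reading is taken in any case, so its information could be used without extra burden on the participant.

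The trial runs 54 weeks in participants aged 10 to 17, and Section 4.2.1.2 includes growth and development in the safety evaluation. Growth velocity is a difference of two heights, so reading error enters it twice. Height enters BMI squared and is the denominator of waist-to-height ratio. What is at stake is the precision of these measures, chiefly for the individual child.

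**Working it through.** The documents give no precision figure for height, so there is no stated value to reproduce. The check sizes the effect of the recording rule.

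**Inputs from the documents.** Two consecutive readings within 2.5 cm, final reading kept (Section 8.2.3); 54 weeks of treatment; 110 ertugliflozin and 55 placebo participants (Section 9.9).

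**Assumptions, not in the documents.** Normal, independent reading errors with SD 0.3 to 1.5 cm; between-child SD of growth velocity 1.5 to 3.0 cm/year; heights 140 to 175 cm; growth velocity taken as (Week 54 height − baseline height) ÷ (54/52.18 years), that is, ÷ 1.035. The visible text gives no formula for growth velocity.

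**Worst case for one accepted pair.** Readings 2.5 cm apart put the final one 2.5/2 = 1.25 cm from the pair mean. At 140 cm this shifts BMI by 1 − (140/141.25)² = 1.8% and waist-to-height ratio by 1 − 140/141.25 = 0.9%. At 175 cm the shifts are 1.4% and 0.7%.

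**Typical error.** If the tolerance rarely binds, the mean of two readings with SD s has SD s/√2, a cut of 1 − 1/√2 = 29%. For larger s the rule itself removes discordant pairs, so it was simulated: readings repeated until two consecutive ones agree within 2.5 cm, then the final reading compared with the mean of the accepted pair. The error SD of growth velocity is the per-visit error SD × √2 ÷ 1.035.

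| Reading SD (cm) | Per-visit error SD, final → mean (cm) | Velocity error SD, final → mean (cm/year) | Cut |
|---|---|---|---|
| 0.3 | 0.30 → 0.21 | 0.41 → 0.29 | 29% |
| 0.5 | 0.50 → 0.35 | 0.68 → 0.48 | 29% |
| 0.9 | 0.84 → 0.65 | 1.15 → 0.89 | 22% |
| 1.5 | 1.26 → 1.12 | 1.73 → 1.54 | 11% |

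**Effect on a group difference.** Reading error adds in quadrature to true variation between children: SE = √(between-child SD² + velocity error SD²) × √(1/110 + 1/55), where the last factor is 0.165. With reading SD 0.5 and between-child SD 1.5:

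- final reading: √(1.5² + 0.68²) × 0.165 = 0.272 cm/year
- mean of pair: √(1.5² + 0.48²) × 0.165 = 0.260 cm/year, about 4% lower

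Over the whole grid the reduction runs from about 0.5% (reading SD 0.3, between-child SD 3.0: 0.500 to 0.498) to about 8% (reading SD 0.9 to 1.0, between-child SD 1.5; at 1.0, 0.322 to 0.298).

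**How often the tolerance acts.** A repeat is triggered in under 0.1% of pairs at reading SD 0.5 cm, about 8% at 1.0 cm and 24% at 1.5 cm.

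**If only later visits were averaged.** With a single-reading baseline and an averaged follow-up, the velocity error SD at reading SD 0.9 is √(0.84² + 0.65²) ÷ 1.035 = 1.03 cm/year, against 1.15: a cut of about 10% instead of 22%.

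**The case against.** The case against acting is substantial, and most of it limits the point without removing it.

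- **No formal analysis depends on height.** Section 9.6.2 gives Tier 3 parameters point estimates by group only, and BMI percentile and waist-to-height ratio are exploratory. This stands. A reader might infer that the rule biases the growth comparison or weakens a planned test of growth. The documents support neither: the trial is double-blind, the same rule applies in both arms, and no between-group interval or test of growth velocity is planned.
- **The tolerance does not measure precision.** From "do not differ by more than 2.5 cm from each other" a reader might infer a reading SD near 0.9 cm (2.5/1.96/√2) and a velocity error of 1.23 cm/year falling to 0.87. That treats a limit for gross disagreement as the actual error, and it ignores the removal of discordant pairs. Given the stadiometer and positioning instructions, real error may be much smaller. At 0.3 cm the velocity error is 0.41 cm/year.
- **Errors within a visit may be shared.** Averaging does not remove error common to both readings from device, examiner or posture, so the percentage cuts are upper figures.
- **The tolerance might seem to need matching to the 1 cm used for waist.** Nothing in the documents supports that figure for height. With independent errors it adds essentially no precision once the pair is averaged: per-visit error SD is 0.37 cm with a 1 cm limit against 0.36 with 2.5 cm at reading SD 0.5, and 1.11 against 1.13 at 1.5.
- **The other reading may not be lost.** Section 8.2.3 does not bar keeping it, and Section 10.1.9 asks for complete source documents. The word final could also mean the settled value after the agreement check. Both are fair, and the second is itself a reason to make the sentence explicit.
- **It is late.** Section 9.9 states that all randomized participants have completed Phase A or left the study during it. Baseline heights are therefore already collected, and a change confined to later visits would yield less than half the gain at a reading SD of 0.9 cm or below.

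**Conclusion.** The point holds as a minor one. Section 8.2.3 takes at least two height readings and records only the last, out of line with weight, waist and blood pressure, without a stated reason. The result is avoidable random error in growth velocity, BMI percentile and waist-to-height ratio. The primary and key secondary A1C analyses, the sample size and the type 1 error are not affected.

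The gain lies mainly in individual values; group means change little. These sizes rest on the assumed reading SDs, independent errors within a pair, an assumed between-child SD and a two-point definition of growth velocity.

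**What to change.** Amend Section 8.2.3 so that both readings of the accepted pair are kept in source and their mean is entered in the eCRF, as Section 8.2.1 does for weight. Use that mean for BMI, waist-to-height ratio and growth velocity. This costs one sentence and an eCRF instruction, with no additional measurement. The 2.5 cm tolerance can stay.

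For heights already collected, retrieve the earlier reading of each accepted pair from source. Before unblinding, use the mean where both readings are available at baseline and follow-up in both arms. Otherwise keep the recorded value and state the limitation in the clinical study report. The cost is a source check at the sites, worth making only if the second reading was routinely written down.

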• Objective: Among those who up-titrated from ertugliflozin 5 mg/day to ertugliflozin 15 mg/day, to assess the within-group (ertugliflozin and placebo) proportion of participants with A1C <7.0% (53 mmol/mol) at 24 weeks.	• A1C					

Confidential

Objectives	Endpoints
 Objective: To assess the within-group (ertugliflozin and placebo) mean changes from baseline at 24 weeks and 54 weeks for the following endpoints: Body weight and body mass index (BMI) percentile Systolic and diastolic blood pressure Bone biomarkers 	 Body weight and BMI percentile Systolic and diastolic blood pressure Bone biomarkers
Objective: To assess the within-group (ertugliflozin and placebo) mean ertugliflozin exposure at 24 weeks.	Steady state ertugliflozin exposure levels

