5.1 Inclusion Criteria

All laboratory measures (to determine eligibility) must be performed after an overnight fast ≥10 hours in duration. Participants with laboratory screening values/findings not meeting protocol inclusion criteria may, at the discretion of the investigator, have 1 repeat determination performed by the central laboratory. If the repeat value satisfies the criterion, the participant may continue in the screening process. Only the specific laboratory test not meeting the inclusion criterion should be repeated (not the entire panel).

Note: If the period of time between **Screening Visit/Visit 1** (ie, date when the screening laboratory measurements were obtained) and the **Visit 3/Day 1/Randomization** date exceeds 28 days, participants must have all screening laboratory measurements repeated (this includes participants who have had their metformin and/or insulin doses adjusted). If screening laboratory values are repeated, the last laboratory draw/result should be used to evaluate eligibility.

To be eligible for inclusion in this study, the participant must meet all of the following criteria:

At Screening Visit/Visit 1

- 1. Have T2DM as indicated by "yes" answers to all of the following:
 - i. Participant has diabetes diagnosed by one of the following American Diabetes Association (ADA) criteria, eg:
 - a. Laboratory determinations of FPG ≥126 mg/dL (7.0 mmol/L), OR
 - b. Random plasma glucose ≥200 mg/dL (11.1 mmol/L), OR
 - c. 2-hour oral glucose tolerance test (OGTT) plasma glucose ≥200 mg/dL (11.1 mmol/L), OR
 - d. A1C ≥6.5% (48 mmol/mol) test performed using a method that is National Glycohemoglobin Standardization Program (NGSP) certified and standardized to the Diabetes Control and Complications Trial (DCCT) assay.
 - ii. Participant has BMI ≥85th percentile at screening OR

participant has a history of being overweight or obese at time of diagnosis of T2DM.

Note: If the participant does not have a BMI ≥85th percentile at the time of screening, the documentation of overweight or obesity at the time of diagnosis of T2DM must be included in the source documents at the site.

2. Have:

- i. T2DM for ≥ 2 years, OR
- ii. T2DM for <2 years and a fasting C-peptide value >0.6 ng/mL at **Screening Visit/Visit 1**.

Confidential

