- 1) Fit a regression model as $Y_{24} = \beta_0 + \beta_1 * Y_0 + \gamma * X + \text{error}$, where Y_0 and Y_{24} are the placebo group A1C values at Baseline and Week 24, respectively, and X is a matrix for the age and insulin stratum fixed covariates.
- 2) Impute missing Week 24 A1C values for ertugliflozin using the estimated mean from the above model and standard deviation equal to the RMSE from the model.

For participants in the placebo group:

- 1) Fit models according to the intermittent missing data pattern with A1C values from the placebo group only:
 - a. For participants with only Baseline data: $Y_{24} = \beta_0 + \beta_1 * Y_0 + \gamma * X + \text{error}$
 - b. For participants with only Baseline and Week 6 data: $Y_{24} = \beta_0 + \beta_1 * Y_0 + \beta_2 * Y_6 + \gamma * X + \text{error}$
 - c. For participants with only Baseline, Week 6 and Week 12 data: $Y_{24} = \beta_0 + \beta_1 * Y_0 + \beta_2 * Y_6 + \beta_2 * Y_{12} + \gamma * X + error$
- 2) Impute missing Week 24 A1C values for placebo using one of the 3 models above based on the missing data pattern with a mean equal to the mean from the regression model and a standard deviation equal to the RMSE from the model.

Descriptive statistics will be used to summarize the A1C mean change from baseline at Week 24 for the individual ertugliflozin dose arms in the subset of participants who were rerandomized at Visit 5/Week 12. All other continuous efficacy endpoints with the exception

of the 2 key secondary endpoints associated with hypotheses H2 and H3, including the Week 12 A1C change from baseline, will be analyzed following the same cLDA method used for the A1C TE estimand under H1 (combined ertugliflozin doses vs. placebo) and will not be analyzed under the TP estimand.

Week 54

The Week 54 analyses will be based on the same FAS population used for the Week 24 analyses. The statistical models for the analyses at Week 54 will be analogous to those at Week 24, except that no between-group comparisons will be provided for **Week 54**. The efficacy endpoints will be summarized for within-group mean change from baseline with estimates and 95% CIs calculated from the analysis model.

Table 7 summarizes the analysis strategy for primary and secondary efficacy endpoints at Week 24 and at Week 54.

Table 7 Analysis Strategy for Efficacy Variables at Week 24 and at Week 54

Variable	Estimand/Approach	Statistical Method	Missing Data Approach
Primary			

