10.8 Appendix 8: BMI for Age Charts

Sites should follow their approved country-specific BMI-for-age percentile charts, if available (eg, sites within the US will refer to the Centers for Disease Control charts). If an approved country-specific BMI-for-age percentile chart is not available, refer to the WHO charts shown in Figure 2 and Figure 3.

Instructions for obtaining the body mass index-for-age percentile:

- Find the child's age on the horizontal axis
- Find the BMI measurement on the vertical axis (to determine BMI, refer to Section 8.2.4).
- The body mass index-for-age percentile will be at the intersection of the child's age and BMI measurement.

Figure 2 BMI for Age Girls, 5 to 19 Years (Percentiles)

[figure not shown]
World Health
Organization

Ref: [deOnis, M. 2007]

Figure 3 BMI for Age Boys, 5 to 19 Years (Percentiles)

Ref: [deOnis, M. 2007]

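### Change in BMI percentile, an exploratory endpoint, averages values from different national charts on a scale compressed near 100, so its pooled mean is hard to interpret; a centrally derived BMI z-score would serve better

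*Combined protocol and SAP*

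**What the plan says.** - **Reference.** Section 8.2.4, under Efficacy Assessments: "Sites will follow their approved country-specific BMI-for-age percentile charts". Appendix 8 gives the example that "sites within the US will refer to the Centers for Disease Control charts"; where no approved national chart exists, sites "refer to the WHO charts shown in Figure 2 and Figure 3".
- **How the value is obtained.** Appendix 8: "The body mass index-for-age percentile will be at the intersection of the child's age and BMI measurement".
- **Who is enrolled.** Inclusion criterion 1 in Section 5.1 has two routes: "Participant has BMI ≥85th percentile at screening OR" the alternative that the "participant has a history of being overweight or obese at time of diagnosis of T2DM".
- **What is analysed.** Section 3 has an exploratory objective on within-group mean change at 24 and 54 weeks that covers "Body weight and body mass index (BMI) percentile". Table 6 lists both as change-from-baseline endpoints. Section 9.6.1 says the remaining continuous efficacy endpoints "will be analyzed following the same cLDA method used for the A1C TE estimand under H1". That model has treatment, time, their interaction, the age stratum and the insulin stratum, with no term for chart or country. Week 54 has no between-group comparison.
- **What is left open.** Section 9.6.1 defers methods for exploratory objectives to the supplemental SAP, which is not among the documents. The relevant rows of the Schedule of Activities are redacted.

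**The concern.** A local chart is adequate for a yes/no eligibility question. A continuous endpoint averaged over countries asks more of it, and two separate things go wrong.

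First, the same child can have a different percentile, and a different change in percentile, on two references. The pooled mean then averages changes that are not on a common scale.

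Second, a percentile flattens towards 100. In a population largely chosen for high BMI, equal changes in BMI-for-age count for very different amounts, and the heaviest participants contribute least.

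What is at stake is a descriptive result. Sections 2.2.1 and 2.3 report body-weight reduction in adults, and Section 2.3 says it is not known whether the adult effects carry over to children. Those sections speak of body weight, not BMI. In growing 10- to 17-year-olds, however, raw weight is mixed with growth, and BMI percentile is the only listed weight measure indexed to age.

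**Working it through.** The plan states no effect size, SD, alpha or power for BMI percentile, so there is no figure to reproduce. Only the arm sizes (110 and 55, Section 9.9) come from the documents. Every other input below is an assumption.

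**1. Compression.** With percentile = 100·Φ(z), a fall of 0.2 in z moves the percentile by 100·[Φ(z) − Φ(z − 0.2)]:

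| Start z | Percentile before | Percentile after | Fall (points) |
|---|---|---|---|
| 1.3 | 90.32 | 86.43 | 3.89 |
| 2.0 | 97.72 | 96.41 | 1.32 |
| 2.4 | 99.18 | 98.61 | 0.57 |
| 2.8 | 99.74 | 99.53 | 0.21 |

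Compared with z = 1.3, the same change counts 3.89/1.32 = 2.9 times less at z = 2.0, 3.89/0.57 = 6.8 times less at z = 2.4, and 3.89/0.21 = 18.5 times less at z = 2.8. This step needs no trial assumption beyond the normal scale.

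**2. Mixed references.** Suppose two charts differ by 0.2 to 0.4 z (assumed). A child at the 95th percentile on one is at the 92.6th to 89.3rd on the other. The same 0.2 z fall reads as 2.42 points on the first and 3.23 to 4.14 on the second.

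**3. Within-group mean, which is the stated objective.** If z does not change on average but varies with SD 0.3, the expected percentile change is 100·[Φ(z/√(1 + 0.3²)) − Φ(z)]. That is −0.97 points at z = 1.3, −0.50 at z = 2.0 and −0.11 at z = 2.8: a fall with no true change. I simulated 110 participants, with baseline z distributed as N(2.0, 0.6), N(2.2, 0.5) or N(1.8, 0.7) (mean, SD), change independent of baseline, and a paired two-sided 5% test standing in for the cLDA. With no true change, the percentile mean fell significantly in about 24% to 43% of trials; on the z scale a significant fall appears in about 2.5%, as it should. With a true change of −0.15 z, power exceeds 99% on both scales. The within-group harm is distortion, not lost power.

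**4. Between-group contrast at Week 24.** The cLDA could yield one, though any p-value would be nominal (Section 9.6). ANCOVA of change on baseline and treatment, 110 against 55, SD of change 0.3, true effect −0.15 z:

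| Baseline z (mean, SD) | z-score | One chart, percentile | Half on a chart shifted 0.4 z |
|---|---|---|---|
| 1.5, 0.5, truncated at the 85th | 86% | 75% | 76% |
| 2.0, 0.5, truncated at the 85th | 85% | 63% | 66% |
| 2.3, 0.5, truncated at the 85th | 85% | 56% | 59% |
| 2.0, 0.6 | 86% | 59% | 63% |

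For −0.10 z in the three truncated settings, the z-score gives 51% to 52% and the percentile 39%, 34% and 27%. The loss comes from compression. Mixing charts does not lower power; in these settings it rises slightly.

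**The case against.** The strongest reply is that little depends on this endpoint. It is exploratory, has no hypothesis, and lies outside the multiplicity scheme and the sample size. Its objective is within-group, so between-group power answers a question that the plan does not pose. All of this stands, and it is why the power figures are only illustrative and the point is minor.

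The simulations also favour z-scores by construction, because effect and noise are set on the z scale. That stands for the size of the loss. It does not touch the compression in step 1.

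A participant normally stays at one site and so on one chart. Each change is then within one reference, and randomisation removes any expected systematic bias between arms. This too stands. What remains is the averaging of changes across references, which affects meaning.

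The documents do not say that the site's chart reading is the analysed value. The supplemental SAP may already derive it centrally, and exploratory changes may be documented there before unblinding (Section 9). If a central derivation exists, one confirming sentence closes the point. Body weight, waist circumference and waist-to-height ratio are also analysed, so the weight question does not rest on this endpoint alone.

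Two stronger readings are tempting. A reader might infer that mixed charts further reduce sensitivity; the calculation shows no such loss, and none was made for chart-reading error. A reader might also infer that the trial would miss a within-group fall in BMI; under the assumed inputs a fall of 0.15 z is detected on either scale.

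**Conclusion.** The point holds as a minor one about an exploratory endpoint. As the visible text stands, pooled mean change in BMI percentile averages changes from different references, gives most weight to the less obese participants, and can fall with no true change in BMI-for-age. A descriptive between-group contrast would also lose sensitivity: about 85% power on z-scores against roughly 55% to 75% on percentiles, for an effect of −0.15 z.

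The compression is arithmetic. The power figures and the rate of spurious falls rest on assumed baseline BMI, SD of change and effect, none of which the documents give. That most participants sit in the upper tail is an inference from the entry criterion, whose second route admits some who are now below the 85th percentile.

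The documents do not support extending this to the A1C hypotheses or to safety: none of those analyses uses BMI percentile.

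**What to change.** In Table 6 or the supplemental SAP, before unblinding:

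1. Keep country-specific charts for the eligibility check only.
2. Derive BMI-for-age centrally, for every participant and visit, from recorded weight, height, age and sex against one named reference, for example the WHO reference already in Appendix 8.
3. Analyse change from baseline in BMI z-score, and show the centrally derived percentile descriptively.

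The cost is a sentence or two of SAP text and one derivation. Section 8.2 has averaged weight entered in the eCRF and height recorded. Waist-to-height ratio is itself an endpoint at Weeks 24 and 54, so height should be on file at those visits. Section 9.9 indicates that Phase A is over for all randomised participants, so the remedy has to be analytical, as this one is. The small downside is that the analysed value may differ from the percentile a site used for eligibility.
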